6.5 PATIENT-REPORTED OUTCOMES ANALYSES

For PROs, the EORTC QLQ-C30 questionnaire and two additional items will be scored according to the EORTC Scoring Manual.

The primary analysis population for evaluation of PRO assessments will include patients in the ITT population with a baseline PRO assessment and at least one post-baseline PRO assessment.

Data from the physical function scale and the global health status/quality of life will be analyzed as a time to deterioration, which will be compared as secondary efficacy endpoints among treatment groups with use of the log rank test (2-sided). Deterioration will be defined as 1) a decrease of 10 points on a transformed 0 to 100 score from baseline on the physical function score or the global status/quality of life scores, or 2) death, or 3) progression. The HR will be estimated using a stratified Cox proportional hazards model and its 95% CI will be provided.

For each assessment timepoint and for each treatment arm, the mean (and 95% CI) and median (and inter-quartile ranges) of the absolute scores for the EORTC QLQ-C30 and additional items and their changes from baseline (Cycle 1 Day 1), will be calculated.

Exploratory descriptive analyses will be conducted using post-treatment data.

6.6 SAFETY ANALYSES

Safety analyses will be performed on the safety population and will include all randomized patients who received at least one dose of study drug. Summaries will be presented for the safety-evaluable population by treatment arm. For safety analyses, patients will be grouped according to whether any amount of atezolizumab or cobimetinib was received, including when atezolizumab or cobimetinib was received in error. For example, if a patient assigned to Arm C received either cobimetinib or atezolizumab in error, this patient will be grouped to Arm A or Arm B, respectively. If a patient assigned to Arm A received atezolizumab but no cobimetinib at all, then this patient will be grouped to Arm B.

Study drug exposure, including treatment duration, number of doses, and dose intensity, will be summarized for each treatment arm using descriptive statistics.

Verbatim description of adverse events will be mapped to MedDRA thesaurus terms and graded according to NCI CTCAE v4.0. All adverse events that occur during or after the first study drug dose will be summarized by treatment arm and NCI CTCAE grade.

In addition, serious adverse events, severe adverse events (Grade 3, 4, and 5), adverse

events of special interest, and adverse events leading to study drug discontinuation or interruption will be summarized accordingly. Multiple occurrences of the same event will be counted once at the maximum severity. The proportion of patients who experience at least one adverse event will be reported by toxicity term and treatment arm.

Deaths reported during the study treatment period and those reported during the follow-up period after treatment discontinuation will be summarized by treatment arm.

Laboratory data with values outside the normal ranges will be identified. In addition, selected laboratory data and vitals will be summarized by treatment arm.

6.7 PHARMACOKINETIC ANALYSES

PK samples will be collected in this study as outlined in [Appendix 2](#). Cobimetinib and atezolizumab maximum and minimum concentration data (C_{min} and C_{max} , respectively) will be tabulated and summarized (mean, standard deviation, median, range, coefficient of variation [CV%], geometric mean and geometric mean coefficient of variation [CVb%]), as appropriate.

Additional PK and pharmacodynamic analyses will be conducted, as appropriate, based on the availability of data.

6.8 IMMUNOGENICITY ANALYSES

Patients are considered to have treatment-induced ATA responses if they are ATA negative at baseline and then develop an ATA response following study drug administration. Patients are considered to have treatment-enhanced ATA responses if they are ATA positive at baseline and the titer of one or more post-baseline samples is at least 4-fold greater (i.e., ≥ 0.60 titer units) than the titer of the baseline sample. Patients are considered to be negative for ATAs if they are ATA negative at all timepoints. Patients are considered to be treatment unaffected if they are ATA positive at baseline but do not have any post-baseline samples with a titer that is at least 4-fold greater than the titer of the baseline sample.

The immunogenicity analyses will include patients with at least one predose and one postdose ATA assessment, with patients grouped according to treatment received (safety population).

The number and proportion of ATA-positive patients and ATA-negative patients during both the treatment and follow-up periods will be summarized by treatment group. Patients are considered to be ATA positive if they have treatment-induced ATA responses or treatment-enhanced ATA responses. Patients are considered to be ATA negative if they are ATA negative or unaffected by treatment.

The relationship between ATA status and safety, efficacy, and pharmacokinetics will be analyzed and reported descriptively via subgroup analyses.

ATA sampling timepoints are provided in [Appendix 2](#).

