Appendix 1 Schedule of Assessments

Arm A: Cobimetinib Plus Atezolizumab Schedule of Assessments (28-Day Cycle)

	Screening ^a	Cycle 1		Cycle 2		Cycle 3+		Treatment Discontinuation ^b	ATA Visit	Survival FU ^c
Day	-35 to 1	1	15	1	15	1	15	< 30 d after last dose	120 d after last dose	q3m
Informed consent ^d	x									
Demographics	x									
Medical and CRC history	x									
Vital signs ^{e,f}	x	x	x	x	x	x	x			
ECOG PS	x	x		x		x				
Weight	x	x		x		x				
Height	x									
Complete physical examination	x									
Limited physical examination		x ^g		x		x				
Hematology ^h	x	x		x		x				
Coagulation (INR and aPTT)	x									
PK sample for cobimetinib	See Appendix 2									
PK and ATA sample for atezolizumab	See Appendix 2								x	
Serum samples for auto antibody tests		x								
Optional WGS		x								
Chemistry ⁱ	x	x		x		x				
CEA		x		x		x		x		
ECHO/MUGA	x			x		x ^j				

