4.7 IMMUNOGENICITY ANALYSES

The number and percentage of patients with positive serum antibodies to atezolizumab at baseline and postbaseline during the study period will be summarized. Adverse events occurring in patients with positive serum antibodies to atezolizumab will be reviewed. The relationship of the immunogenicity response with pharmacokinetics, safety, and efficacy may also be evaluated when appropriate.

ATA sampling timepoints are provided in [Appendix 3](#).

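### If survival is compared by ever-positive ATA status, immortal time favours the ATA-positive group; the plan should specify a landmark for this exploratory analysis

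*Protocol*

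**What the plan says.** Protocol Section 6.8 commits to the analysis: "The relationship between ATA status and safety, efficacy, and pharmacokinetics will be analyzed and reported descriptively via subgroup analyses". Protocol Section 2.4 makes the effect of ATAs on efficacy, safety and pharmacokinetics an exploratory objective.

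Status is defined after baseline, on an ever-positive rule. Treatment-induced patients are "ATA negative at baseline and then develop an ATA response following study drug administration". Treatment-enhanced patients are positive at baseline and qualify if "the titer of one or more post-baseline samples is at least 4-fold greater" than the baseline titer. On the other side, "Patients are considered to be negative for ATAs if they are ATA negative at all timepoints", and baseline-positive patients without that rise are treatment unaffected and grouped with the negatives. The analysis set is "patients with at least one predose and one postdose ATA assessment". Incidence is to be reported as "The number and proportion of ATA-positive patients and ATA-negative patients during both the treatment and follow-up periods".

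Protocol Appendix 2 and SAP Appendix 3 schedule ATA samples at Day 1 of Cycles 1 to 4, at Cycle 8, every 8 cycles after that, at treatment discontinuation, and 120 ± 30 days later. Protocol Appendix 1 lists the last visit at "120 d after last dose". Survival and progression-free survival are counted from randomisation (Protocol Sections 6.4.1 and 6.4.2).

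The SAP supersedes the protocol for registration (SAP Section 1). Its Section 4.7 says that patients with "positive serum antibodies to atezolizumab at baseline and postbaseline during the study period will be summarized". It makes the evaluation against efficacy optional, and it gives no grouping rule, time origin or method. Neither document mentions a landmark or a time-dependent ATA covariate.

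**The concern.** A patient first found positive at a late sample must have lived to give it and, for the cycle samples, stayed on drug. A patient who dies or stops early has fewer chances to be found positive and remains negative by default. If survival is then compared from randomisation, the positive group is credited with time during which its members could not have died and still been classified that way. This is immortal-time bias, and it comes from the classification rule, not from biology.

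At stake is the reading of the immunogenicity results. Protocol Section 1.4.4 reports ATA-associated pharmacokinetic changes in some patients at lower doses, so the question is a genuine one. An artefact pointing towards better outcome in ATA-positive patients could mislead the answer. Safety has a related problem: longer exposure gives both more ATA samples and more recorded adverse events.

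**Working it through.** **Scale, from the plan's own figures.** ATA status exists only in Arms A and B. Deaths in Arm C: 178 + 127 − 235 = 70. Deaths in A and B: 235 − 70 = 165, as in SAP Section 2.4.2. The minimum detectable hazard ratio (HR) for A versus B (2:1 allocation) is exp(−1.96/√(165 × 2/9)) = 0.72, also as stated. The protocol's 0.60 titer units for a 4-fold rise is log10(4) = 0.602. None of these figures is in dispute.

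**Inputs from the documents.** The sampling schedule above; cycles of 28 days (Arm A) and 21 days (Arm B); median survival of 6.4 or 10.5 months (Protocol Section 6.1); the ever-positive rule; at least one postdose sample.

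**Inputs assumed, because the documents give none.** 20% or 40% of patients eventually convert; conversion times are exponential with mean 10, 30, 90 or 180 days (median = mean × ln 2, so about 7, 21, 62 and 125 days); treatment duration has a median of 2 or 4 months independent of survival, or is tied to survival; administrative censoring is at 11 to 23 months.

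**Method.** 60 scenarios of 100,000 simulated patients, with survival exponential and unaffected by ATAs, so the true HR is 1.00. The Cox HR for ever-positive versus negative is taken from randomisation. For comparison, a landmark at day 84 keeps everyone alive at that day and fixes status from samples up to then.

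| Mean onset (median) | From randomisation, treatment independent of survival | From randomisation, treatment tied to survival | Day-84 landmark, independent | Day-84 landmark, tied |
|---|---|---|---|---|
| 10 d (7 d) | 0.96–0.99 | 0.93–0.95 | 0.98–1.01 | 0.97–0.98 |
| 30 d (21 d) | 0.83–0.91 | 0.79–0.87 | 0.97–1.01 | 0.89–0.95 |
| 90 d (62 d) | 0.69–0.74 | 0.64–0.66 | 0.99–1.01 | 0.84–0.92 |
| 180 d (125 d) | 0.63–0.70 | 0.57–0.58 | 0.98–1.02 | 0.83–0.92 |

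The HR from randomisation was below 1 in all 60 scenarios. One example uses the Arm B schedule, true median survival of 10.5 months for everyone, 40% converting, median treatment of 2 months and mean onset of 90 days. The apparent medians are 13.6 months (positive) and 10.1 months (negative), HR 0.73.

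A separate simulation with 200,000 patients per scenario, treatment duration independent of survival apart from truncation at death, and conversion set by its median gave 0.92–0.93 at 14 days, 0.81–0.83 at 30 days, 0.72–0.75 at 60 days and 0.65–0.70 at 120 days.

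**Which landmark works.** Cycle 3 Day 1 is day 1 + 2 × 28 = 57 in Arm A and 1 + 2 × 21 = 43 in Arm B. When treatment length tracks survival, a landmark near these days that requires only being alive still gives 0.85–0.91. Patients who stopped early are no longer sampled, stay in as negatives, and have shorter survival. Also requiring an ATA sample at the landmark visit gives 0.98–1.02, because everyone compared has then had the same opportunity to test positive. A time-dependent ATA covariate gives 0.98–1.02 when treatment is independent of survival and 0.90–0.97 when it is tied.

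**The case against.** The strongest reply is that the governing document does not plan this comparison. SAP Section 4.7 makes it optional, and SAP Section 4.4.6 does not name ATA status among its subgroups (that list is open-ended). The protocol calls the objective exploratory and the reporting descriptive, and it does not itself specify an HR from randomisation by ATA status. This stands, and it limits the importance of the point. It does not remove it: Protocol Section 6.8 still commits to the analysis, SAP Section 2.2.6 lists a possible correlation with efficacy among the outcome measures, and a descriptive HR or Kaplan-Meier plot is biased in the same way as a tested one.

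A second reply is that requiring one postdose sample already removes the earliest immortal time. That is correct, and it is why the bias is small when nearly all conversion appears at the first postdose samples. It does nothing about conversion first seen later.

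A third reply concerns the remedy. A landmark turns late converters into negatives and drops patients with early events, and for adverse events it would discard everything in Cycles 1 and 2, including early infusion reactions. This also stands, and the fix below is shaped by it.

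**Conclusion.** This is a cheap improvement to an exploratory analysis. If survival or progression-free survival is compared from randomisation by ever-positive ATA status, the comparison is biased towards better outcome in ATA-positive patients even when ATAs have no effect. For survival, the HR under no effect is about 0.9 or higher if nearly all conversion is seen by the first postdose samples, and about 0.55 to 0.75 if median conversion is at 60 to 120 days. These sizes rest on assumed conversion timing and treatment duration. The primary test, alpha and power are not affected.

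A reader might infer three stronger things that the documents do not support:

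- **That ATA-positive patients will certainly appear to live longer.** The bias has a known direction, but its size depends on timing that is not given, and other confounding may add to it or offset it.
- **That a real loss of efficacy would be hidden.** This is possible in principle, but every simulation here was run with no ATA effect, so it has not been shown.
- **That the SAP overstates treatment-emergent ATA.** SAP Section 4.7 reports positivity at baseline and post-baseline and makes no treatment-emergent claim. What it lacks is the protocol's definitions: a baseline-positive patient without a 4-fold rise is negative under Protocol Section 6.8 but can appear in the SAP's post-baseline count.

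**What to change.** In Protocol Section 6.8 and SAP Section 4.7:

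1. State that any survival or progression-free survival comparison by ATA status will use a landmark at an early scheduled sample, for example Cycle 3 Day 1. Limit it to patients still at risk (alive or, for progression-free survival, progression-free) who have an ATA sample at that visit. Fix status from samples up to then and count time from the landmark.
2. Allow a time-dependent ATA covariate as a sensitivity analysis.
3. Keep ever-positive status for the incidence table.
4. Do not landmark the adverse-event summaries. Report them with exposure and with onset relative to the first positive sample.
5. Carry the treatment-induced, treatment-enhanced and treatment-unaffected definitions into SAP Section 4.7.

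The work is SAP and protocol wording and a small amount of programming; no new data are needed. The statistical cost is real. Patients who die or leave treatment before the landmark are excluded. Later seroconverters count as negative: 45–69% of ever-positive patients in simulations with median conversion at 60 to 120 days. Precision and sensitivity to late-onset ATA effects therefore fall. For progression-free survival, the Arm A landmark (day 57) coincides with the first 8-week scan (± 1 week), so patients who progress at that scan may be excluded; the Arm B landmark (day 43) comes before it. These limits should be stated beside the result.

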6.9 EXPLORATORY BIOMARKER ANALYSES

Exploratory biomarker analyses will be performed in an effort to understand the association of these markers with study drug response, including efficacy and/or adverse events. The blood and tumor biomarkers include but are not limited to NGS, PD-L1, and CD8, as defined by IHC, qRT-PCR, or other methods. Additional pharmacodynamic analyses will be conducted as appropriate.

7. DATA COLLECTION AND MANAGEMENT

7.1 DATA QUALITY ASSURANCE

The Sponsor will be responsible for data management of this study, including quality checking of the data. Data entered manually will be collected via EDC through use of eCRFs. Sites will be responsible for data entry into the EDC system. In the event of discrepant data, the Sponsor will request data clarification from the sites, which the sites will resolve electronically in the EDC system.

The Sponsor will produce an EDC Study Specification document that describes the quality checking to be performed on the data. Central laboratory and other non-EDC system-captured data will be sent directly to the Sponsor, using the Sponsor's standard procedures to handle and process the electronic transfer of these data.

eCRFs and correction documentation will be maintained in the EDC system's audit trail. System backups for data stored by the Sponsor and records retention for the study data will be consistent with the Sponsor's standard procedures.

7.2 ELECTRONIC CASE REPORT FORMS

eCRFs are to be completed through use of a Sponsor-designated EDC system. Sites will receive training and have access to a manual for appropriate eCRF completion. eCRFs will be submitted electronically to the Sponsor and should be handled in accordance with instructions from the Sponsor.

All eCRFs should be completed by designated, trained site staff. eCRFs should be reviewed and electronically signed and dated by the investigator or a designee.

At the end of the study, the investigator will receive patient data for his or her site in a readable format on a compact disc that must be kept with the study records. Acknowledgement of receipt of the compact disc is required.

7.3 ELECTRONIC PATIENT-REPORTED OUTCOME DATA

An electronic device will be used to capture PRO data. The data will be transmitted to a centralized database maintained by the electronic device vendor.

Once the study is complete, the data, audit trail, and trial and system documentation will be archived. The investigator will receive patient data for the site in both human- and machine-readable formats on an archival-quality compact disc that must be kept with the study records as source data. Acknowledgement of receipt of the compact disc is required. In addition, the Sponsor will receive all data in a machine-readable format on a compact disc.

7.4 SOURCE DATA DOCUMENTATION

Study monitors will perform ongoing source data verification to confirm that critical protocol data (i.e., source data) entered into the eCRFs by authorized site personnel are accurate, complete, and verifiable from source documents.

Source documents (paper or electronic) are those in which patient data are recorded and documented for the first time. They include, but are not limited to, hospital records, clinical and office charts, laboratory notes, memoranda, patient-reported outcomes, evaluation checklists, pharmacy dispensing records, recorded data from automated instruments, copies of transcriptions that are certified after verification as being accurate and complete, microfiche, photographic negatives, microfilm or magnetic media, X-rays, patient files, and records kept at pharmacies, laboratories, and medico-technical departments involved in a clinical trial.

Before study initiation, the types of source documents that are to be generated will be clearly defined in the Trial Monitoring Plan. This includes any protocol data to be entered directly into the eCRFs (i.e., no prior written or electronic record of the data) and considered source data.

Source documents that are required to verify the validity and completeness of data entered into the eCRFs must not be obliterated or destroyed and must be retained per the policy for retention of records described in Section 7.6.

To facilitate source data verification, the investigators and institutions must provide the Sponsor direct access to applicable source documents and reports for trial-related monitoring, Sponsor audits, and IRB/EC review. The study site must also allow inspection by applicable health authorities.

7.5 USE OF COMPUTERIZED SYSTEMS

When clinical observations are entered directly into a study site's computerized medical record system (i.e., in lieu of original hardcopy records), the electronic record can serve as the source document if the system has been validated in accordance with health authority requirements pertaining to computerized systems used in clinical research. An acceptable computerized data collection system allows preservation of the original entry of data. If original data are modified, the system should maintain a viewable audit trail that shows the original data as well as the reason for the change, name of the person making the change, and date of the change.

7.6 RETENTION OF RECORDS

Records and documents pertaining to the conduct of this study and the distribution of IMP, including eCRFs, ePRO data, Informed Consent Forms, laboratory test results, and medication inventory records, must be retained by the Principal Investigator for at least 15 years after completion or discontinuation of the study, or for the length of time required by relevant national or local health authorities, whichever is longer. After that period of time, the documents may be destroyed, subject to local regulations.

No records may be disposed of without the written approval of the Sponsor. Written notification should be provided to the Sponsor prior to transferring any records to another party or moving them to another location.

8. ETHICAL CONSIDERATIONS

8.1 COMPLIANCE WITH LAWS AND REGULATIONS

This study will be conducted in full conformance with the ICH E6 guideline for Good Clinical Practice and the principles of the Declaration of Helsinki, or the laws and regulations of the country in which the research is conducted, whichever affords the greater protection to the individual. The study will comply with the requirements of the ICH E2A guideline (Clinical Safety Data Management: Definitions and Standards for Expedited Reporting). Studies conducted in the United States or under a U.S. Investigational New Drug (IND) application will comply with U.S. Food and Drug Administration regulations and applicable local, state, and federal laws. Studies conducted in the European Union (E.U.) or European Economic Area will comply with the E.U. Clinical Trial Directive (2001/20/EC).

8.2 INFORMED CONSENT

The Sponsor's sample Informed Consent Form will be provided to each site. If applicable, it will be provided in a certified translation of the local language. The Sponsor or its designee must review and approve any proposed deviations from the Sponsor's sample Informed Consent Forms or any alternate consent forms proposed by the site (collectively, the "Consent Forms") before IRB/EC submission. The final IRB/EC-approved Consent Forms must be provided to the Sponsor for health authority submission purposes according to local requirements.

If applicable, the Informed Consent Form will contain separate sections for any optional procedures. The investigator or authorized designee will explain to each patient the objectives, methods, and potential risks associated with each optional procedure. Patients will be told that they are free to refuse to participate and may withdraw their consent at any time for any reason. A separate, specific signature will be required to document a patient's agreement to participate in optional procedures. Patients who decline to participate will not provide a separate signature.

The Consent Forms must be signed and dated by the patient or the patient's legally authorized representative before his or her participation in the study. The case history or clinical records for each patient shall document the informed consent process and that written informed consent was obtained prior to participation in the study.

The Consent Forms should be revised whenever there are changes to study procedures or when new information becomes available that may affect the willingness of the patient to participate. The final revised IRB/EC-approved Consent Forms must be provided to the Sponsor for health authority submission purposes.

Patients must be re-consented to the most current version of the Consent Forms (or to a significant new information/findings addendum in accordance with applicable laws and IRB/EC policy) during their participation in the study. For any updated or revised Consent Forms, the case history or clinical records for each patient shall document the informed consent process and that written informed consent was obtained using the updated/revised Consent Forms for continued participation in the study.

A copy of each signed Consent Form must be provided to the patient or the patient's legally authorized representative. All signed and dated Consent Forms must remain in each patient's study file or in the site file and must be available for verification by study monitors at any time.

For sites in the United States, each Consent Form may also include patient authorization to allow use and disclosure of personal health information in compliance with the U.S. Health Insurance Portability and Accountability Act of 1996 (HIPAA). If the site utilizes a separate Authorization Form for patient authorization for use and disclosure of personal health information under the HIPAA regulations, the review, approval, and other processes outlined above apply except that IRB review and approval may not be required per study site policies.

